### **Subgroup analyses**

Subgroup analyses will be conducted comparing PFS between Arm A versus Arm B in the following subgroups of the FAS (but not limited to):

- Age at randomization (< 65 versus  $\geq$  65)
- Sex (male versus female)
- ECOG (0-1 versus 2)
- IGHV mutation status (mutated versus non-mutated)
- Region/Country (China versus other)
- Rai stage at screening (Stage 0-II versus III-IV)
- $\beta$ 2-microglobulin at baseline ( $\leq$  3.5 mg/L versus  $>$  3.5 mg/L)
- Bulky disease (longest diameter of lymph node  $<$  5 cm versus  $\geq$  5 cm at baseline)
- Presence of 11q deletion.
- Complex karyotype (Yes versus No)

The HR and corresponding 95% CI for each subgroup will be calculated based on an unstratified Cox proportional hazards model with treatment as the only covariate. The Cox models will be fitted using SAS® PROC PHREG with the Efron method to control for ties, using the by statement to obtain HR and 95% CI for each subgroup level separately. These hazard ratios and associated two-sided 95% CIs will be summarized and presented on a forest plot, along with the results of the overall primary analysis. Separate analyses will be run for each subgroup, i.e. subgroup levels will not be treated as strata. The subgroup analyses for the stratification factors will be based on the values entered into the IRT/RTSM, all other factors will be based on values recorded on the eCRF.

Other baseline variables may also be assessed if there is clinical or biological justification or an imbalance is observed between the treatment arms. The purpose of the subgroup analyses is to assess the consistency of treatment effect across expected prognostic factors. If a baseline imbalance is observed between treatment arms, ad-hoc subgroup analysis may be used to investigate any potential for impact on the main results.

Unless there is a marked difference between the results of the statistical analyses of the PFS from the BICR data and that of the site investigator tumor data, these subgroup analyses will only be performed on the PFS endpoint using the BICR data.

No adjustment to the significance level for testing of the subgroup and sensitivity analyses will be made since all these analyses will be considered supportive of the analysis of PFS.

KM plots of PFS by treatment and 11q deletion status/IGHV mutational status will be produced as supportive figures.

#### 4.2.2.3 Overall response rate

ORR (assessed by BICR per IWCLL 2018 criteria) will be compared between treatment arms (Arm A versus Arm B) using the Cochran-Mantel-Haenszel (CMH) chi-square test, adjusted for randomization stratification factors ECOG (0-1 versus 2) and Rai stage (Stage 0-II versus III-IV).

Summaries will be produced that present the number and percentage of patients with a tumor response (CR, CRi, nPR, PR) based upon the number of patients in the FAS per BICR assessments alongside the CMH p-value, the odds ratio and its 95% CI.

The analysis of ORR will be repeated using investigator responses. The overall response (CR+CRi+nPR+PR) and CR/CRi concordance rate will also be summarized separately.

As supportive analysis, ORR+PRL using BICR assessments and investigator assessments will be analyzed in the same manner as ORR.

#### 4.2.2.4 Best overall response

For each treatment arm, best overall response (BOR) will be summarized by n (%) for each category (CR, CRi, nPR, PR, PRL, SD, PD and UNK) with tables and figures as appropriate. No formal statistical analyses are planned for BOR.

#### 4.2.2.5 Duration of response

DoR as assessed by BICR per IWCLL 2018 criteria will be analyzed using the methods described in [Section 4.2.2.1](#). Only patients with a BOR of CR, CRi, nPR or PR in the FAS will be included in this analysis.

The DoR will be repeated using investigator derived responses.

#### 4.2.2.6 Time to next therapy

TTNT will be analyzed using the methods described in [Section 4.2.2.1](#).

The status of patients at the time of analysis will be summarized. This will include the number (%) of patients who are known to have received a subsequent therapy, the number (%) of patients who died prior to receiving a subsequent therapy, and the number (%) of patients who discontinued the study prior to starting a new therapy and were alive at the date of discontinuation. The subset of patients who discontinued the study prior to death will be further summarized by the number (%) of patients who were lost to follow-up prior to starting a subsequent therapy and the number (%) of patients withdrew consent prior to starting a new therapy.

In patients who received a subsequent anti-cancer therapy, a summary table of the first subsequent anti-cancer therapy by treatment arm will be provided, as well as response to first subsequent anti-cancer therapy by treatment arm (if available).

#### 4.2.2.7 Overall survival (OS)

OS will be analyzed using the methods described in [Section 4.2.2.1](#).

The status of patients at the time of analysis will be summarized. This will include the number (%) of patients who died, the number (%) still in survival follow-up and the number (%) of patients who discontinued the study prior to death. Patients who discontinued the study prior to death will be further broken down by presenting the number (%) of patients who discontinued voluntarily, the number (%) of patients lost to follow-up and the number (%) of patients who discontinued the study for any other reason.

A sensitivity analysis for OS will also be performed where patients who received crossover therapy will be censored one day prior to the first dose of crossover therapy.

The number of patients prematurely censored will be summarized by treatment arm. A patient would be defined as prematurely censored if their survival status was not defined at the DCO.

In addition, duration of follow-up will be summarized using medians:

- In all patients: time from randomization to the date of death (i.e. overall survival) or to the date of censoring (date last known to be alive) for censored patients regardless of treatment arm.

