6.8 Crossover

At investigator discretion, subjects randomized to Arm B who have BICR-confirmed disease progression and meet eligibility for crossover may have the option to receive acalabrutinib monotherapy as crossover treatment provided the informed consent of the crossover treatment is signed. After the final analysis and per Amendment 5.0, subjects can cross over with investigator-assessed PD with agreement from medical monitor/study physician prior to the conclusion of the study. Screening assessments for crossover listed in Table 3 should be performed within the screening time window of 42 days (as the EoT/SFU visit or its corresponding tests in terms of schedule may overlap with the crossover screening visit or its corresponding tests, the EoT/SFU visit and its corresponding tests can be waived in such case, e.g. the tests or assessments are scheduled both in EoT/SFU window and crossover screening window. CT scans that showed disease progression from Arm B can be used for the crossover screening CT scan, if within 60 days of crossover dosing Cycle 1 Day 1). Eligibility for crossover includes the following criteria:

- Crossover candidates must have BICR-confirmed or investigator-assessed disease progression.

- ECOG performance status and the laboratory parameters as outlined in the inclusion criteria #4 and #7, and exclusion criteria #8 should be met. See Section 5.1 and Section 5.2.
- There are no concerns by the investigator judgement including but not limited to safety risks, compliance, restrictions and study process requirements.

Crossover candidates may not receive any other anticancer therapy to treat CLL, including acalabrutinib outside the study, from the last dose of Arm B treatment to the initiation of crossover therapy with acalabrutinib. Should a subject develop a second primary malignancy while on trial, crossover option after curative treatment of the second primary malignancy may be considered after discussion with the study physician. Crossover subjects will be treated with acalabrutinib until disease progression based on investigator assessment or unacceptable toxicity. BICR assessment is not required for crossover subjects.

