9.5.1.5 Overall survival

OS will be analysed in the same fashion as that for primary efficacy endpoint PFS as described in Section 9.5.1.1.

A sensitivity analysis will be performed. Patients who receive crossover therapy will be censored at the date before first dose date of the crossover therapy.

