### **3. PRIMARY AND SECONDARY VARIABLES**

#### **3.1 Handling of crossover patients**

Patients in Arm B who have BICR-confirmed progression will have the option to crossover to acalabrutinib. For all efficacy analyses, except for the analysis of OS, will include data prior to crossover. OS will encompass the entire study duration.

All safety analyses, except that for death, will include data prior to crossover unless noted otherwise. Death will be summarized in the following three ways: over the randomized period, crossover period and entire study duration.

The crossover period is defined only for patients who were randomized and received at least one dose of crossover therapy.

Prior to crossover first/last dose refers to the first/last dose of chlorambucil/rituximab. Post crossover first/last dose refers to the first/last dose of acalabrutinib.

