**Table 7 Formal Statistical Analyses to be Conducted and Pre-planned Sensitivity Analyses**

Endpoints Analyzed	Notes
PFS	
Primary analysis: Stratified log-rank test adjusted for ECOG (0-1 versus 2) and Rai stage (Stage 0-II versus III-IV) with BICR defined response
 
Sensitivity analyses a
 
 
1. Unstratified log-rank test
 
2. Analysis of alternative censoring rule - without censoring prior to subsequent therapies
 
3. Analysis of alternative censoring rule – without censoring prior to two or more consecutively missed response evaluations
 
4. Ascertainment bias analysis - using investigator assessments
 

Overall response rate	CMH chi-square test adjusted for ECOG (0-1 versus 2) and Rai stage (Stage 0-II versus III-IV) using both BICR and investigator defined responses
Duration of response	Stratified log-rank test adjusted for ECOG (0-1 versus 2) and Rai stage (Stage 0-II versus III-IV) using both BICR and investigator defined responses
Time to next therapy	Stratified log-rank test adjusted for ECOG (0-1 versus 2) and Rai stage (Stage 0-II versus III-IV)
Overall survival	
Stratified log-rank test adjusted for ECOG (0-1 versus 2) and Rai stage (Stage 0-II versus III-IV)
 
Sensitivity analysis considering censoring crossover patients prior to receiving acalabrutinib monotherapy

Minimal residual disease	CMH chi-square test adjusted for ECOG (0-1 versus 2) and Rai stage (Stage 0-II versus III-IV)

a See 4.2.2.2 for further details

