#### **Hazard ratio and confidence interval estimation**

Time-to-event endpoints will be analyzed using a 2-sided stratified log-rank test adjusting for ECOG (0-1 versus 2) and Rai stage (Stage 0-II versus III-IV) for generation of the p-value.

The stratification variables in the statistical modelling will be based on the values entered into IRT/RTSM at randomization, even if it is subsequently discovered that these values were incorrect.

HR will be calculated from a stratified Cox proportional hazards model together with its corresponding, 95% CI. Treatment is the only covariate, ties are handled by the Efron approach and the CI is calculated using a profile likelihood approach.

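### Does the overall-survival sensitivity analysis that censors Arm B patients at crossover need to be changed, given that this censoring is probably informative?

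*SAP*

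**What the plan says.** The main OS analysis ignores crossover: SAP 3.1 states that "OS will encompass the entire study duration", and SAP 3.3.6 counts deaths whatever later therapy was given.

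One sensitivity analysis is added. SAP 4.2.2.7 says "patients who received crossover therapy will be censored one day prior to the first dose of crossover therapy". Protocol 9.5.1.5 gives the same rule: "Patients who receive crossover therapy will be censored at the date before first dose date of the crossover therapy". SAP Table 7 lists it as "Sensitivity analysis considering censoring crossover patients prior to receiving acalabrutinib monotherapy". None of the three states an assumption, names a target quantity or says how to read the result beside the main analysis.

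Protocol 6.8 sets out who may cross over: "At investigator discretion, subjects randomized to Arm B who have BICR-confirmed disease progression and meet eligibility for crossover may have the option". Fitness is also required: "ECOG performance status and the laboratory parameters as outlined in the inclusion criteria #4 and #7, and exclusion criteria #8 should be met". So is the investigator's agreement: "There are no concerns by the investigator judgement including but not limited to safety risks, compliance, restrictions and study process requirements". From Amendment 5.0, after the final analysis, investigator-assessed progression is enough.

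The model is a stratified log-rank test with a Cox model for the HR (SAP 4.2.2.1): "Treatment is the only covariate, ties are handled by the Efron approach".

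**The concern.** Censoring is harmless to a log-rank test or Cox model only if, within arm and stratum, censored patients have the same later risk of death as those who remain. The crossover rules make that doubtful. Only Arm B patients are censored, and only after progression. Removing progressed patients lowers the apparent death rate in Arm B and pulls the HR (A versus B) toward 1 or beyond. Selecting the fitter progressors leaves the frailer ones at risk and pulls it the other way. Baseline ECOG and Rai stage capture neither progression nor fitness at progression.

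The likely use of the analysis is comparison with ITT OS. A reader might take agreement as proof that crossover did not matter, or disagreement as a measure of how much it did. Neither inference is safe. The SAP shows awareness of informative censoring, but only for PFS by central review (SAP 4.2.2.2).

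**Working it through.** **Is there a plan figure to reproduce?** No. The documents give no OS effect, death count, OS power or crossover rate. Their PFS power and alpha figures do not bear on this point.

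**Inputs from the documents.** PFS medians 30 and 90 months, 75 patients per arm, 30-month accrual (Protocol 9.2, SAP 1.3); final analysis at about 45 months (Protocol 4.4).

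**Inputs assumed.** Monthly death hazard before and after progression, share of Arm B progressors who cross over, delay from progression to crossover, effect of crossover on later death, and strength of fitness selection.

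**Method.** Illness-death simulation, 600,000 per arm. Progression hazard = ln 2 / median PFS − pre-progression death hazard. With 0.002 before progression this is 0.0231 − 0.002 = 0.0211 in Arm B and 0.0077 − 0.002 = 0.0057 in Arm A. Strong selection means half the progressors have 0.25 times and half 1.75 times the post-progression hazard, crossing with probability 0.9 and 0.1. The HR is from a Cox model with treatment only.

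| Setting (death hazard before/after progression; share crossing; selection; mortality ratio after crossover; delay) | No-crossover HR | ITT HR | Censored HR |
|---|---|---|---|
| A: 0.002/0.015; 70%; none; 1; 0 months | 0.576 | 0.576 | 0.927 |
| A with delay 6 months | 0.571 | 0.571 | 0.734 |
| A with delay 12 months | 0.574 | 0.574 | 0.653 |
| B: 0.002/0.015; 50%; none; 0.31; 1.4 months | 0.568 | 0.731 | 0.732 |
| C: 0.004/0.008; 50%; strong; 1; 1.4 months | 0.861 | 0.861 | 0.815 |
| D: 0.002/0.015; 50%; strong; 0.31; 1.4 months | 0.593 | 0.658 | 0.589 |
| E: 0.003 throughout; 50%; none; 1; 1.4 months | 0.999 | 0.999 | 1.001 |

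**Reading the table.**
- A: crossover does nothing, yet the censored HR is off by 0.927 − 0.576 = +0.351. The error falls to 0.734 − 0.571 = +0.163 and 0.653 − 0.574 = +0.079 as the delay grows, partly because fewer patients have crossed by the cut-off. Protocol 6.8 gives a 42-day screening window but no maximum interval from progression.
- B: crossover works, and the two analyses agree (0.731 and 0.732) while both miss 0.568.
- C: the direction reverses, 0.815 − 0.861 = −0.046.
- D: the planned analysis comes close to the no-crossover HR, and ITT does not.
- E: with no rise in death risk after progression, there is no bias.

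Size and direction therefore depend on inputs the documents do not supply. The largest error needs no fitness selection, which the eligibility rules make less likely.

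**Size against the noise.** In setting A with no delay, 150 patients give 17.2 expected deaths, of which 5.3 are removed by censoring. The approximate 95% factor is exp(1.96 × 2/√D). For ITT this is exp(3.92/√17.2) = 2.6; for the censored analysis, exp(3.92/√11.9) = 3.1. The shift is ln(0.927/0.576) = 0.48 on the log scale, about half the ITT half-width of 0.95. Across the settings examined, 11 to 23 deaths are expected, with factors of 2.5 to 3.6 in trial-size runs. In three of four trial-size settings, the mean log shift between the two analyses was under half its standard deviation (+0.01 against 0.16, −0.05 against 0.11, +0.03 against 0.24). In the fourth, close to setting A, it was +0.45 against 0.33.

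**Strata.** SAP 4.2.2.1 requires two events per arm in every stratum; secondary endpoints that still fall short after pooling are analysed unstratified. Four strata × two arms × 2 = 16 deaths at the least, and well spread. With equal strata and HRs of 0.57 to 1.0, all eight cells reach two deaths in 0% of draws at 11 deaths and 5% to 9% at 23. Two-factor stratification of OS is unlikely, so the assumption would hold within arm and within whatever strata remain, possibly none.

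**What is already planned.** Disposition separately for crossover therapy (SAP 4.2.7); deaths over the randomized period, the crossover period and the whole study (SAP 3.1); first subsequent therapy by arm (SAP 4.2.2.6).

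**The case for a change.** The strongest reply is that a caution costs almost nothing. Comparison with ITT is the main use of this analysis, unlabelled agreement invites a claim of robustness, and the SAP already warns of informative censoring elsewhere. Patients may still cross over until about 54 months (Protocol 4.4 and 6.8), so a later OS update could censor more of them. Low precision is itself a reason for caution.

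The statistical part of this stands. The censoring is probably informative, and neither agreement nor disagreement with ITT measures the crossover effect. It does not show that the plan needs changing. The plan makes no false statement: it does not call the result crossover-adjusted and draws no inference from it. The final analysis has already been conducted (Protocol 1.2 and 4.4), so a sentence added now would affect interpretation only, and the study report can carry it.

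Replacing the analysis is not supported either. Only about 9 to 18 Arm B progressors are expected not to cross over, with about 1 to 6 deaths among them, too few for a two-stage model. No gain in accuracy at this size has been shown for a rank-preserving structural failure time model.

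**Conclusion.** No change to the plan. The concern is correct as statistics but identifies missing interpretive detail, not a defect that alters a result. ITT OS remains the main OS analysis, alpha control covers PFS only (SAP 4.2.1), and study success is defined on PFS (Protocol 9.1).

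Under the assumptions above, the censored HR can differ from the no-crossover HR by about −0.05 to +0.35, and can also match it. The documents cannot narrow that range, because they give no death hazards, crossover rate, delay or degree of selection. With 11 to 23 deaths expected under those assumptions, neither OS HR could carry a strong reading. A statistician writing the report would call the censored analysis descriptive and read it beside the planned crossover and death counts. That is ordinary reporting practice and needs no amendment.

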#### 4.2.2.8 Minimal residual disease negative rate

Peripheral blood MRD negative rate at cycle 9 will be compared between treatment arms (Arm A versus Arm B) using the CMH chi-square test, adjusted for randomization stratification factors.

#### 4.2.2.9 Improvement of disease-related symptoms and sustained hematologic improvement

##### Disease-related symptoms

Constitutional symptoms include weight loss, fever, night sweats, and fatigue. For each symptom number and percentage of subjects with symptom absent at each post-baseline timepoint will be summarized in the subset of subjects with symptoms present at baseline.

##### Sustained hematologic improvement

Sustained hematologic improvement is defined as hematologic improvement that persisted continuously for  $\geq 56$  days (8 weeks) without blood transfusion or growth factors. This sustained improvement requires that 1) two assessments meet the improvement criteria and are at least 56 days apart, 2) all assessment(s) with non-missing data between those two assessments must meet the improvement criteria, and 3) there is no concomitant use of blood transfusion/growth factor during this time period. The proportion of subjects achieving sustained hematologic improvement in the subset of subjects with cytopenia(s) at baseline, prior to subsequent anticancer therapy, will be summarized by treatment arm.

Cytopenia is defined as at least one of the following 3 criteria being met:

- Neutropenia:  $ANC \leq 1.5 \times 10^9/L$
- Anemia:  $Hgb \leq 11 \text{ g/dL}$
- Thrombocytopenia: platelet count  $\leq 100 \times 10^9/L$ .

Hematologic improvement in the subset of patients with cytopenia(s) is defined as follows for each parameter:

- Improvement to hemoglobin  $> 11 \text{ g/dL}$  from baseline or increase  $\geq 50\%$  over baseline.
- Improvement to platelet counts  $> 100 \times 10^9/L$  from baseline or increase  $\geq 50\%$  over baseline.
- Improvement to  $ANC > 1.5 \times 10^9/L$  or increase  $\geq 50\%$  over baseline.

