**Table 3 Response Assessment Criteria for CLL (modified from [Hallek 2018](#)) – IWCLL Criteria**

Group	Parameter	CR a,b	PR c	PD	SD
A	Lymph nodes (target lesions only d )	None $\geq 1.5$ cm	Decrease $\geq 50\%$ (from baseline) e	Increase $\geq 50\%$ from baseline or from response	Change of -49% to +49%
	Liver and/or spleen size f	Spleen size <13 cm; liver size normal	Decrease $\geq 50\%$ (from baseline)	Increase $\geq 50\%$ from baseline or from response	Change of -49% to +49%
	Constitutional symptoms	None	Any	Any	Any
	Circulating lymphocyte count	Normal	Decrease $\geq 50\%$ from baseline	Increase $\geq 50\%$ over baseline	Change of -49% to +49%
B	Platelet count	$\geq 100,000/\mu\text{L}$	$\geq 100,000/\mu\text{L}$ or increase $\geq 50\%$ over baseline	Decrease of $\geq 50\%$ from baseline secondary to CLL	Change of -49% to +49%
	Hemoglobin	$\geq 11.0$ g/dL (untransfused and without erythropoietin)	$\geq 11$ g/dL or increase $\geq 50\%$ over baseline	Decrease of $\geq 2$ g/dL from baseline secondary to CLL	Increase < 11.0 g/dL or < 50% over baseline, or decrease > 2 g/dL
	Marrow	Normocellular, no CLL cells, no B-lymphoid nodules	Presence of CLL cells, or of B-lymphoid nodules, or not done	Increase of CLL cells by $\geq 50\%$ on successive biopsies	No change in marrow infiltrate

Abbreviations: CLL=chronic lymphocytic leukemia; CR=complete response; CT=computed tomography; PD=progressive disease; PR=partial response; SD=stable disease.

Note: CR, complete response: all of the criteria have to be met; PR, partial response: for a PR at least 1 of the parameters of group A and 1 parameter of group B need to improve if previously abnormal. If only one parameter of both groups A and B is abnormal prior to therapy, only 1 needs to improve. PD, progressive disease: at least one of the above criteria of group A or group B has to be met; SD, stable disease: all of the above criteria have to be met. Constitutional symptoms alone do not define PD.

- a CRi (CR with incomplete bone marrow recovery) refers to patients who fulfill all the criteria for a CR (including the bone marrow examinations), but have a persistent anemia, thrombocytopenia, or neutropenia apparently unrelated to CLL, but related to drug toxicity.
- b nPR (Nodular partial response): CR with the presence of B-lymphoid nodules in the bone marrow which reflect residual disease.

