## 4.2 Analysis Methods

The following table (Table 7) details which endpoints are to be subjected to formal statistical analysis, together with pre-planned sensitivity analyses, making it clear which analysis is regarded as primary for that endpoint.

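### Sustained hematologic improvement (SAP 4.2.2.9) can be scored on a 50% rise in a count that was normal at baseline, while the low count stays low

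*SAP*

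**What the plan says.** SAP 4.2.2.9 builds the measure in three steps.

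- **Who is analyzed.** "Cytopenia is defined as at least one of the following 3 criteria being met": ANC at or below 1.5 x10^9/L, hemoglobin at or below 11 g/dL, or platelets at or below 100 x10^9/L. The reported quantity is "The proportion of subjects achieving sustained hematologic improvement in the subset of subjects with cytopenia(s) at baseline", before subsequent anticancer therapy and by arm. It is a single proportion in a single any-cytopenia subset.
- **What counts as improvement.** The bullets open with "Hematologic improvement in the subset of patients with cytopenia(s) is defined as follows for each parameter". Each has two limbs joined by *or*: exceed the threshold (hemoglobin 11 g/dL, platelets 100, ANC 1.5), or rise by at least 50% over baseline. The hemoglobin and platelet bullets contain the words "from baseline or increase", which link the threshold limb to the baseline value. The ANC bullet has no such link on its threshold limb.
- **What counts as sustained.** The rule needs that "two assessments meet the improvement criteria and are at least 56 days apart", that every non-missing assessment between them also qualifies, and that no transfusion or growth factor is used in that period.

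For comparison, the partial-response note under SAP Table 3 does tie improvement to an abnormal starting value: "1 parameter of group B need to improve if previously abnormal".

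**The concern.** A patient enters the subset because at least one count is low, and the other two may be normal. The measure is meant to show whether the low count recovered. As written, the improvement rule covers all three counts for everyone in the subset, and nothing limits a rule to patients low on that count. If a normal count can supply the improvement, the numerator includes patients whose cytopenia has not changed.

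At stake is the meaning of a by-arm efficacy summary in an open-label trial. The reported proportion would mix recovery from cytopenia with upward variation in counts that needed no recovery.

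**Working it through.** The plan states no rate for this measure, so there is no figure to reproduce. The check has three parts.

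**1. Limb by limb, for a count that is normal at baseline.**

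Threshold limb: the improvement cut-offs (>11, >100, >1.5) are the exact complements of the cytopenia cut-offs (≤11, ≤100, ≤1.5). A count already above its cut-off has nothing to improve to, so the limb can reasonably be taken as confined to low counts.

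50% limb: the condition is on-study value ≥ 1.5 x baseline, with no condition on the baseline.

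| Count | Normal baseline | Value needed (1.5 x baseline) |
|---|---|---|
| Hemoglobin, g/dL | 11.1 | 16.65 |
| Hemoglobin, g/dL | 13 | 19.5 |
| Platelets, x10^9/L | 101 | 151.5 |
| Platelets, x10^9/L | 180 | 270 |
| ANC, x10^9/L | 1.6 | 2.4 |
| ANC, x10^9/L | 3.0 | 4.5 |

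From a normal start the hemoglobin values are practically out of reach. The platelet and ANC values are not, so the gap lies in those two counts.

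Test patient: hemoglobin 9, platelets 180, ANC 3.0 at baseline. Hemoglobin and platelets stay flat and ANC rises to 4.5 for at least 56 days without transfusion or growth factor. Since 4.5 ≥ 1.5 x 3.0, the written rule scores this patient as improved. A rule tied to the low count does not, because hemoglobin is still 9.

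**2. Same parameter across 56 days.** The sustained rule refers to the improvement criteria collectively. Hemoglobin could qualify at the first assessment and platelets at the last, with one or the other at each visit between. The written conditions are then met although neither count stayed improved for 56 days.

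**3. Size.** The documents give no baseline count distributions and no within-patient variability, so every input below except the visit days is an assumption.

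- Visits: days 8 to 673, from the hematology schedule in Protocol Table 1.
- True values, stable over time: hemoglobin mean 11.5, SD 1.8; platelets median 140, log-SD 0.45; ANC median 4, log-SD 0.5.
- Within-patient coefficient of variation (CV): hemoglobin 3-4%, platelets 10-15%, ANC varied. Visit noise is log-normal, with one baseline draw.
- No treatment effect. Improvement in any one parameter suffices, because the SAP does not say whether one or all low counts must improve. Sustained status is judged within one parameter, so the table isolates the 50% limb. Transfusion and growth-factor use are not modeled.

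In both columns the threshold limb applies only to low counts.

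| Assumed ANC CV | 50% limb open to normal counts | Both limbs tied to the low count | Difference (points) |
|---|---|---|---|
| 10% | 18.1% | 18.0% | 0.1 |
| 15% | 21.7% | 20.0% | 1.7 |
| 25% | 32% | 22% | 10 |
| 35% | 47% | 31% | 16 |

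A repeat run agreed to within one percentage point in every cell. It used hemoglobin and platelet CVs of 3% and 10% in the first three rows and 4% and 15% in the last, so the last step is not due to ANC alone. With no treatment effect, the excess is noise around a single baseline value: a low baseline draw makes later values look like a 50% rise.

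**The case against.** The strongest reply is that the text already implies the tie. The bullets speak of improvement to a level, the cut-offs mirror the cytopenia definitions, and the preceding item in 4.2.2.9 summarizes each symptom among patients who had symptoms at baseline. A sensible programmer may well have coded it that way. This stands for the threshold limb. It does not reach the 50% limb, which nothing in the section restricts.

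Three stronger readings are tempting, and the documents do not support them.

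- A reader might infer that almost every patient counts as improved, because normal counts sit above their thresholds at every visit. That requires ignoring the word improvement: an unchanged normal count has not improved.
- A reader might infer that hemoglobin, platelet and ANC rows are diluted by patients who cannot improve on that count. The SAP specifies one proportion and no per-parameter rows or denominators. A patient with normal platelets or ANC can also still meet the 50% limb.
- A reader might infer that a true difference between arms would vanish. The simulation contains no treatment effect, so it says nothing on that.

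The objection on importance also stands. Table 7, which "details which endpoints are to be subjected to formal statistical analysis", does not list this measure. It is not among the primary or secondary endpoints, and trial success rests on PFS alone.

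**Conclusion.** The point holds in limited form. Under the 50% limb as written, a sustained rise in a normal ANC or platelet count makes a patient a responder while the cytopenic count stays low. The 56-day rule also does not require the same parameter throughout.

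The effect is to overstate the reported proportion. The excess is about 0 to 16 percentage points over assumed ANC CVs of 10% to 35%, and negligible at the low end. That range rests on the assumed distributions and variability and on the absence of a treatment effect. The direction rests on the wording alone: opening the limb to normal counts can add responders but not remove any. The effect on the difference between arms is not established.

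Severity is low. The measure is a descriptive by-arm summary, and PFS, its alpha and its power are untouched.

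**What to change.** In SAP 4.2.2.9, state that improvement on either limb counts only for a parameter that met its own cytopenia criterion at baseline: hemoglobin ≤11 g/dL, platelets ≤100 x10^9/L, ANC ≤1.5 x10^9/L. Require the same parameter to qualify at both assessments and at all those between. Say whether improvement in one low parameter is enough or all must improve. If per-parameter rates are shown, use the patients low on that parameter as the denominator.

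The protocol synopsis treats the 03 January 2024 data cut-off as the final analysis. The practical step is therefore to confirm which derivation was programmed, state it with the result, and rerun the summary if the 50% limb was left open.

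The cost is one clause in the SAP and a small programming change. The reported proportions may be less favorable.
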